Treatment dosage and duration are based on prescribing information and prior successful clinical trial weight loss results.^{31,110} The placebo-control group is an essential arm in this trial as study measures can change over time without drug intervention and it supports the evaluation of efficacy and safety. The drug and placebo kits will be supplied by AstraZeneca, or the current pharmacologic company responsible for ExQW. Exenatide vials or pens 2.0 mg powder for injection will be supplied. All subjects will have weekly phone calls when not coming for a study visit, to check adherence and any potential

adverse effects. Any evidence for adverse effects will be discussed with the PI of each site and safety clinical visits will be considered.

All study medication will be stored/locked in the investigational pharmacy under appropriate temperature conditions. Dispensing and accountability records will be maintained by appropriate staff members.

Analysis

Analysis plan and sample size calculations by Aim.

The research team includes personnel with statistical and data management expertise for overseeing data collection, storage methods, and the following analyses (see letter of support, [name]). Adherence data collected during the placebo run-in phase will be summarized descriptively. All subjects completing the run-in phase will go on to the randomized treatment phase. The primary analyses will use the intention-to-treat (ITT) approach; i.e., subjects will be analyzed according to their randomized assignment regardless of treatment received. In addition, data of all completers will be analyzed separately as a sensitivity analysis. While every attempt will be made to collect complete data and retain all subjects, all sample size and power calculations account for dropout. Statistical methods have been selected to allow for inclusion of partial data. All testing is two-sided and $\alpha=0.05$. Repeated measures analyses will be conducted using SAS (SAS Institute, Inc., Cary, NC, USA) or R (The R Foundation for

Statistical Computing).

Analysis populations: All eligible subjects randomized will be included in the ITT population. The ITT population will be the primary analysis population for all primary, secondary, and tertiary outcomes. The safety population will be the primary population for all safety analyses, and include all subjects who receive at least one dose of study drug or placebo.

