Table 1. Summary of Study Measures and Outcomes and Their Use in the Proposed Research

Measure	Domain	Instrument	Aim	Role/Application
$\Delta\text{BMI}\%$	Adiposity	Anthropometry	1	Primary outcome
Total body fat mass	Body composition	DEXA	1	Secondary outcome
Fat and total calorie intake	Post test meal satiety assessment	Free buffet meal analysis	1	Secondary outcome
Glucose tolerance	Glucose tolerance, MetS	Glucose at 0', 120' (OGTT)	2	Secondary outcome
HDL, triglycerides	MetS	Fasting lipids	2	Secondary outcome
hsCRP	Inflammation	hsCRP at fasting time point	2	Secondary outcome
Free living EE	Energy homeostasis	Doubly labeled water	3	Tertiary outcome
Energy intake	Energy intake	24h dietary recall (ASA24)	3	Tertiary outcome
Leptin, adiponectin, sOB-R, α -MSH, HOMA-IR, WBISI	Energy homeostasis, leptin sensitivity, and insulin resistance	Baseline and stimulated hormones	3	Tertiary outcomes and predictors

Aim 1: To test effects of GLP1RA on hypothalamic obesity prospectively.

Sample: Available anthropometry measures will be included in the analyses (see also Fig. 1 below).

Primary outcome analysis: For efficacy analysis the primary outcome is % change in BMI from week 0 (baseline) to 36 wk. A piecewise (separating the randomized and run out phases) linear mixed-effects model¹¹¹ will be fit with % change in BMI from baseline to 36 wk as the outcome; treatment, time, and the interaction between treatment and time as factors of interest; and randomization stratification variables (site, age, and gender) included as covariates. This model is a generalization of analysis of covariance (ANCOVA) that allows all follow-up repeated measures to be included.

Table 2. Additional Descriptive Parameters, Predictors and Covariates used in Study

Measure	Domain	Instrument	Aim
ΔBMI , ΔBMI z-score	Adiposity	Anthropometry	1
Subjective appetite	Hunger and fullness rating	Visual analog scale	1
Syst. & diast. BP	CVD risk factor, MetS	Ambulatory BP	2
Exercise	Physical activity measure	Actigraphy ^{112,113}	3
Energy intake	Energy intake	24h dietary recall	3
Eating behavior	Assessment of overeating and food reward	Overeating (CEBQ), ⁷⁶ & hyperphagia. ⁷⁷	3
Brain lesion score, hypothalamic region and residual lesion volumes	Structural lesion in the pituitary-hypothalamic area	Brain MRI images	3

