3a: Test GLP1RA treatment on energy homeostasis. Sample: All available EE and energy intake measures from DLW analyses and ASA24 dietary recalls at 0 and 36 wk will be included in the analyses (see Fig. 1). Tertiary outcomes analysis: The tertiary outcomes are change in EE and energy intake from baseline to 36 wk. Separate analyses will be conducted for EE and energy intake. For example for EE, an ANCOVA will be used to model the outcome of change in EE from baseline to 36 wk post-treatment with treatment as the factor of interest and Δ BMI and Δ energy intake included as covariates as both might affect EE independently of drug. A similar ANCOVA will be used to model the outcome of change in energy intake from baseline to 36 wk. Exploratory analyses will examine the change of energy intake after 6 and 18 wk of treatment to estimate effect sizes and inform the design of future studies.

Sample size and power: Assuming a normal distribution of differences, a type I error of 0.05, and a dropout rate of up to 20%, a final evaluable sample size of 19 subjects per group will provide 85% power to detect relative changes (average change divided by the pooled standard deviation (SD) of the change) in EE in relation to energy intake or energy intake in relation to EE of approximately 1 between the two groups. Based on preliminary pooled data from Ambler¹¹⁴ and Eliakim¹¹⁵ et al., the observed

pooled SDs of EE per DLW measures were 162 kcal/d and 155 kcal/d, respectively. Assuming a moderate correlation between baseline and follow-up measures ($r=0.5$), this would correspond to detectable differences of one pooled SD, or 162 kcal/d and 155 kcal/d, respectively. Expected results and benchmarks for success (exploratory efficacy endpoints): We expect that GLP1RA will lead to increased EE adjusted for Δ BMI and Δ energy intake.

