3b: Determine predictors of GLP1RA treatment success. Sample: Pretreatment metabolic parameters and EE measures from DLW analyses (see Fig. 1), and all available outcomes measures will be included in the analyses (collected at 0 and 36 wk). Outcome measures and exploratory analyses: Potential predictors will be considered one at a time. Potential predictors include a hypothalamic lesion score; hyperphagia; EE; and the metabolic predictors leptin, adiponectin, sOB-R, α -MSH, HOMA-IR, WBISI including a leptin/Ob-R ratio.²⁰⁴ In addition to examining the relationship between the post-surgery lesion score (=standard approach for all subjects) and the response to GLP1RA treatment, we will perform a measurement study using high resolution images that would allow parcellation of the hypothalamus and surrounding areas. We expect that we will obtain images in the required high resolution quality in a subgroup of patients (50%; $n=24$). We will use these images for exploratory volumetric as well as topographic studies and will test if lesion volume or deficiencies in certain brain areas are associated with obesity outcomes or response to treatment using analyses similar to those described for lesion score. These exploratory measurement studies may be important for generating future hypotheses. A linear mixed-effects model will be fit with % change in BMI from baseline to follow-up as the outcome; treatment, time, the interaction between treatment and time, the potential predictor, and interactions between the potential predictor and treatment, time and treatment x time as factors of interest. Covariates and within-subject correlation matrix are as described for Specific Aim 1. Exploratory analyses will examine eating behavior and fat and total calorie intake as additional covariates. A contrast based on the interaction between the potential predictor and treatment x time will be used to estimate the direction and magnitude of the potential predictor on treatment response at 36 wk. Predictors will be standardized to be unitless, dividing by the SD to rank magnitudes and compare across predictors.

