5. SUBJECTS

Subjects

It is anticipated approximately 16 participants will be treated per year (5-6 per study site) during the first three years of the study. We expect to screen 80 subjects to get 48 subjects enrolled and 38 to complete the study (potential dropout rate of rate of 20%). Subjects will be between the ages of 10-25 y old at time of enrollment (11-27 y at end of intervention), and we expect each patient to complete the 56 week study.

Recruitment

We will recruit patients from the endocrinology clinics at the three sites, and will accept referrals from other endocrine providers. We will be advertising the study to other Pediatric Endocrinologists through a secure message board.

Enrollment

The PI at each site will screen and consent/assent subject or designate other qualified study staff to do so. Qualified participants will start with a 2-week placebo run-in to test adherence to the protocol. Immediately afterwards, subjects will be assigned treatment using a permuted-block randomization (1:1) with varying block sizes constructed by the Children's Core for Biomedical Statistics (CCBS) of Seattle Children's Research Institute (SCRI) stratified by study site, two age groups (10-14y, 15-25y), and gender. This is a double-blind study (participants and investigators both blinded). The study statistician will be blinded as well; a second statistician not involved in the conduct of the study will be responsible for the final preparation of the randomization scheme. Only the independent CCBS statistician and dispensing pharmacy at each site will know assigned study medications. It is anticipated approximately 16 participants will be treated per year (5-6 per study site) during the first three years of the study. We expect to screen 80 subjects to get 48 subjects enrolled and 38 to complete the study (potential dropout rate of rate of 20%). As we would expect many of these participants to be prepubertal as they have hypogonadotropic hypogonadism by virtue of their disease, pubertal status will not be used as an inclusion or exclusion criteria for the study.

Inclusion Criteria

- Age 10-25 years at time of enrollment
- Diagnosis of hypothalamic obesity with age- and sex adjusted BMI $\geq 95\%$ or BMI $\geq 30 \text{ kg/m}^2$ if over 18 y
- History of craniopharyngioma or another tumor located in the hypothalamic area
- Hypothalamic lesion documented by neuroradiology
- ≥ 6 months post-surgical or radiation treatment

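### The Aim 3a models for energy expenditure and energy intake omit the randomisation strata that the Aim 1 and Aim 3b models include: a conservative error, modest in size and cheap to correct.

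*Combined protocol and SAP*

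**What the plan says.** Section 5 (Enrollment) describes "permuted-block randomization (1:1) with varying block sizes", "stratified by study site, two age groups (10-14y, 15-25y), and gender". With three sites this makes 3 × 2 × 2 = 12 cells for 48 patients.

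Section 4 (Analysis) treats these variables differently by aim:

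- **Aim 1:** the primary mixed model has "randomization stratification variables (site, age, and gender) included as covariates".
- **Aim 2:** continuous secondary endpoints are analysed by methods similar to the primary one.
- **Aim 3b:** "Covariates and within-subject correlation matrix are as described for Specific Aim 1".
- **Aim 3a:** change in energy expenditure is modelled "with treatment as the factor of interest and Δ BMI and Δ energy intake included as covariates". For intake, "A similar ANCOVA will be used to model the outcome of change in energy intake from baseline to 36 wk". Neither sentence names site, age or gender.

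No general statement in the Analysis section extends the strata to every model. For Aim 3a the plan also states that "a final evaluable sample size of 19 subjects per group will provide 85% power" for a difference of about one SD of the change.

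**The concern.** Blocking within strata balances the arms on site, age group and gender, and so removes part of the between-stratum variation from the true sampling error of the treatment difference. A model without the strata leaves that variation in its residual. When the strata predict the outcome, the reported standard error is then too large, the interval too wide and the test conservative.

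A programmer working from the Aim 3a text would leave the strata out, because that text gives its own covariate list where Aim 3b refers back to Aim 1. At stake is precision in a data set of about 38 evaluable patients. Leaving the covariate set open also allows a choice between adjusted and unadjusted results once the data are seen.

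**Working it through.** **The plan's own figure.** With 19 per group, a difference of 1 SD and two-sided alpha 0.05, the noncentrality is 1 × √(19/2) = 3.08 on 36 df. Power is 85.1% by the noncentral t (86.9% by the normal approximation). The stated 85% reproduces. It describes a plain two-group comparison with no covariates.

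**Simulation of the Aim 3a model.**

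- From the plan: 48 randomised 1:1 within 12 cells, 38 evaluable, direct treatment effect of 0 or 1 SD, alpha 0.05.
- Assumed: blocks of 2 or 4 (the plan gives no sizes); equal chance of each site, age group and gender; dropout at random; strata acting additively and explaining a share R² of the residual variance. ΔBMI and Δ intake are in the model, each with coefficient 0.3. Treatment shifts both by either nothing or 1 SD. For BMI, 1 SD is in line with the relative effect of -1.12 in Table 3.
- Residual df: 38 - 4 = 34 without strata. Site costs 2, age group 1 and gender 1, leaving 30 with them.
- 3,000 trials per cell. The SE ratio, null rejection and CI columns come from the runs with no treatment effect, and the power column from those with a 1 SD effect.

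| R² | Shift in ΔBMI and Δ intake | Model SE / true SE, no strata | Null rejection, no strata | CI half-width in SD, without → with strata | Power, without → with strata | Change (points) |
|---|---|---|---|---|---|---|
| 0 | none | 0.988 | 5.3% | 0.676 → 0.697 | 82.5% → 80.2% | -2.3 |
| 0 | 1 SD | 0.979 | 5.7% | 0.835 → 0.872 | 65.8% → 61.2% | -4.6 |
| 0.1 | none | 1.022 | 4.5% | 0.680 → 0.665 | 83.1% → 84.0% | +0.9 |
| 0.1 | 1 SD | 1.019 | 4.3% | 0.835 → 0.825 | 65.3% → 65.7% | +0.4 |
| 0.2 | none | 1.043 | 3.8% | 0.678 → 0.624 | 84.1% → 88.6% | +4.5 |
| 0.2 | 1 SD | 1.041 | 4.2% | 0.836 → 0.780 | 64.5% → 70.1% | +5.6 |
| 0.3 | none | 1.094 | 3.2% | 0.680 → 0.585 | 82.8% → 90.7% | +7.9 |
| 0.3 | 1 SD | 1.064 | 3.7% | 0.836 → 0.728 | 64.8% → 75.2% | +10.4 |

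With the strata in the model, the SE ratio is 0.96 to 1.01 throughout and null rejection is 4.6 to 5.7%.

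**Simulation error.** Near 65% power it is √(0.65 × 0.35 / 3000) = 0.9 points per rate. Repeating the power cells with 12,000 trials each moved the two outlying changes towards the rest (the 4.6-point fall became 3.4, the 5.6-point gain 5.0). The others stayed within half a point.

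**Other settings.**

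- With ΔBMI shifted by 1 SD and intake by 0.5 SD, power without and with strata is 71.3% and 68.5% at R² = 0, 71.2% and 71.0% at 0.1, 73.1% and 78.2% at 0.2, and 73.7% and 82.5% at 0.3.
- A 20,000-trial run with neither covariate shifted gives 83/83/84/85% without strata and 81/84/88/92% with them, and unadjusted null rejection of 2.9% at R² = 0.3. The mean SE with strata, relative to without, is 1.03, 0.97, 0.91 and 0.85.

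**Interval width.** At R² = 0.1 the table gives 1 - 0.665/0.680 = 2.2% and 1 - 0.825/0.835 = 1.2%. At 0.3 it gives 1 - 0.585/0.680 = 14.0% and 1 - 0.728/0.836 = 12.9%. The 20,000-trial SE ratios correspond to 3% and 15%. If the plan's 162 kcal/d is taken as the residual SD, the half-width at R² = 0.3 with no shift goes from 0.680 × 162 = 110 to 0.585 × 162 = 95 kcal/d.

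**The case against.** **The size rests on an assumed R².** The outcome is within-person change, which removes between-person differences in level, and the model then conditions on two further changes. A reader might infer that, because kcal/d differ across ages 10 to 25 and between the sexes, the strata must matter here. That argument concerns levels, and the documents do not show that the strata predict change. This objection stands: at 10% the benefit is close to nil, and at zero there is a small loss.

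**No stated property is breached by the omission.** A reader might infer that the test is invalid. It is not: the error is conservative, and no false-positive claim follows. A reader might also set the stated 85% against about 93% with strata at R² = 0.3. That gain applies only to a comparison without ΔBMI and Δ intake, which is not the Aim 3a model. The powers of about 65 to 74% seen when treatment shifts those covariates come mainly from adjusting for post-randomisation variables, which is a separate matter. Adding strata does not turn that coefficient into a total treatment effect.

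**The text may be illustrative.** The energy expenditure model is introduced as an example, so a reader who infers a deliberate decision to drop the strata goes beyond the text. A drafting gap is the more natural reading, but the gap still has to be closed, because nothing else in the plan closes it.

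**Conclusion.** The omission is real and its direction is clear: where the strata predict change, the Aim 3a models as written overstate the standard error. Across the assumed 10 to 30%, the sizes are those in the working: a few per cent on the standard error, and an interval that could be narrower by anything from a negligible amount to about one seventh. The gain in power becomes worthwhile only from about 20%.

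These figures depend on additive stratum effects, random dropout and small blocks. Sparse cells and dropout leave some imbalance, which limits the overstatement and explains why adjustment costs a little when the strata are uninformative. Since Table 1 lists both outcomes as tertiary, this is a minor improvement in consistency and precision, and not a threat to the trial's conclusions.

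**What to change.** Add one sentence to the Aim 3a analysis: both ANCOVAs, for change in energy expenditure and for change in energy intake, will include site, age group and gender as covariates, as in Aim 1. Fix this before unblinding.

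The cost is 4 degrees of freedom and, if the strata turn out to explain nothing, the small loss of power shown above. The variables are already recorded for every randomised patient, so no new data or design change is needed.

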3. INTRODUCTION

Background/Significance

Excessive weight gain and its cardiometabolic sequela are frequent complications of hypothalamic tumors, a condition known as hypothalamic obesity (HO). Most tumors in this region are craniopharyngiomas (CP),¹ which constitute 5–9% of childhood brain tumors.^{2,3} Patients with CP typically become obese and have more features of the metabolic syndrome compared to matched controls.^{4,5} Overall, a 3-19-fold higher cardiovascular mortality had been reported,^{6,7} and a recent nationwide population-based study in Sweden demonstrated increased rates for cerebral infarction (7-fold), death due to cerebrovascular diseases (5-fold), and type 2 diabetes mellitus (6-fold) in CP patients in comparison to the general population.⁸ Thus, early and effective management of obesity is vital for this population,⁹ which is more resistant to treatment than uncomplicated obesity.¹⁰⁻¹⁸ Recognized risk factors for severe obesity include large hypothalamic tumors or lesions affecting several medial and posterior hypothalamic nuclei that impact satiety signaling pathways.^{19, 26-28} Structural damage in these nuclei often lead to uncontrolled appetite, rapid weight gain, central insulin and leptin resistance, decreased sympathetic activity, low energy expenditure (EE), and increased energy storage in adipose tissue.^{13,19} Recently, our group developed a *semi-quantitative assessment of hypothalamic damage on brain magnetic resonance imaging (MRI) to predict the risk for HO development in CP*.²⁶

Previous results of treating HO with a glucagon-like-peptide-1 receptor agonist (GLP1RA) in rats²⁰ and humans^{21,22} provide promising proof-of-principle data to support our randomized clinical trial. Our primary hypothesis is that drugs causing weight loss via intact hindbrain signaling pathways offer a desperately needed option for treatment of HO, even in very obese HO subjects with severe hypothalamic damage. Induction of weight loss by GLP1RAs is believed to be related to multiple mechanisms involving the gastrointestinal tract, vagus nerve, and the brain leading to increased satiety.²³⁻²⁸ Peripheral administration of GLP-1 or GLP1RA reduces blood glucose and energy intake in humans and rodents, and long-term treatment results in loss of body weight.^{23,29-45} Critically, we do not know whether GLP1RA treatment affects EE and activity,⁴⁶⁻⁴⁹ or whether the site and size of brain lesions affect responses to GLP1RA treatment.

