4. STUDY DESIGN AND METHODOLOGY

Specific Aims and Hypotheses

Specific Aim 1: To test effects of GLP1RA on hypothalamic obesity prospectively. *We hypothesize that treatment with GLP1RA will significantly reduce adiposity in patients with HO. We furthermore hypothesize that GLP1RA treatment will lead to increased satiety.* To this end, we propose to conduct a double blind, placebo-controlled, randomized trial of once weekly extended release exenatide (ExQW) on metabolic and clinical outcomes. Following baseline testing, 48 patients (10-25y at time of enrollment) with HO will be randomly assigned with equal allocation to ExQW or matching placebo injection for 36 weeks, followed by an 18-week open label extension during which all patients will receive ExQW. Our primary endpoint is percent change in BMI after 36 weeks. Secondary endpoints will include changes in body fat, and satiety by free buffet meal test.

Specific Aim 2: To determine effects of GLP1RA on cardiometabolic risk factors. *We hypothesize that GLP1RA will also lead to (1) favorable changes in blood glucose, lipid profile, and inflammatory marker, and (2) reduced insulin secretion during an oral glucose tolerance test.* In the same cohort, we will examine changes in blood glucose, lipid profile, inflammatory markers, and insulin resistance by testing insulin secretion during an oral glucose tolerance test after adjustment for glucose response and adiposity.

Specific Aim 3: To explore additional outcome measures, and predictors of treatment responses. HO represents a disorder of energy homeostasis.

Aim 3 A: *To test the hypothesis that GLP1RA will normalize homeostasis by increasing EE in relation to energy intake.* This and prior hypotheses allow us to test potential predictors of treatment outcomes.

Aim 3 B: *To test the hypotheses that (1) a lower hypothalamic lesion score and (2) lower fasting serum leptin as well as (3) higher pretreatment hyperphagia will be associated with better BMI outcomes.*

The study will include brain lesion scoring, behavioral and hormonal measures, free-living total daily energy expenditure by doubly labeled water (DLW), energy intake by 24h dietary recall, and activity by actigraphy.

Overview/Scope

Study Design

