Energy expenditure measures. There is no previous study examining the impact of GLP1RA treatment on EE in subjects with CP, a population suffering from decreased resting metabolic rate and physical activity.⁵³⁻⁵⁶ **Total daily energy expenditure** (total EE, kcal/day) will be measured using doubly labeled water (DLW). Total EE comprises resting metabolic rate, thermic effect of meals, and physical activity EE. All three components can be accurately determined by using the gold standard method, DLW under free living conditions over a period of two wk.^{57,58} Through periodic urine collection, DLW estimates carbon dioxide production by measuring the elimination of the tracers deuterium (²H) and oxygen-18 (¹⁸O) from the body.⁴⁷ The DLW is a reference method for measurements of average total EE for a period of 10-14 days in free-living individuals tested in a variety of pediatric⁵⁹⁻⁶¹ and adult⁶² populations, and individuals with various diseases.⁶³⁻⁶⁵ The DLW protocol will be coordinated by the Energy Balance Laboratory at Vanderbilt University ([name] – Director, see letter of support) in collaboration with the Gas-Isotope-Ratio Mass Spectrometry Laboratory at Baylor College of Medicine's USDA/ARS Children's Nutrition Research Center (DLW Lab - Dr. [name], Director). Participants from all sites will receive a DLW sample and will collect urine according to the protocol schedule. Baseline urine samples will be collected at the clinic visits while day 7 and day 14 samples will be mailed from home. After drinking the doubly labeled water at the site, subjects will be instructed to rinse the glass and to drink the rinse water; they will be asked to repeat this step (rinsing and drinking a total of two times). They will be asked to void and the urine sample will be discarded. The next two patient voids (at 2 hours and 6 hours) will be collected for isotope analysis (deuterium and ¹⁸O) at Baylor University. Urine samples will be collected at day 7 and day 14 for isotope analysis.

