between treatment and time will be used to specifically test for a significant difference in % change in BMI from baseline to 36 wk post-treatment and 54 wk (end of open label extension). Additionally, descriptive summaries will be prepared for change in BMI z-score to supplement interpretation of findings. Study outcomes, their use, and descriptive parameters are in Tables 1 & 2.

Table 3 Aim	Outcome	Observed Δ Exenatide vs. Control	Observed pooled Std. Dev.	Observed relative effect size
1	% ΔBMI	-4.29	3.84	-1.12
1	Absolute ΔBMI	-1.74	1.25	-1.39
2	$\Delta\text{Glucose AUC}$ (per 100)	-29.36	26.44	-1.11
2	$\Delta\text{Insulin}$ (mU/L)	-7.62	7.14	-1.07

Sample size and power: Table 3 shows observed relative effect sizes in our preliminary study for the between-treatment comparison of change from baseline to 3 mo (data from previous study²²). Assuming a normal distribution of changes, a type I error rate of 0.05, and a dropout rate of up to 20%, a sample size of 24 subjects per group (19 evaluable) will provide 85% power to detect relative treatment effect sizes of 1 or greater (in absolute value) for % change in BMI, which is consistent with the preliminary data.

Expected result: We expect GLP1RA treatment will reduce BMI (primary efficacy endpoint). Further we expect that GLP1RA treatment will reduce total body fat mass and increase satiety (assessed by hunger VAS as well as fat and total calorie intake at free buffet test meal).

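### Aim 3a: the only stated energy-expenditure model adjusts for post-randomisation changes, no total-effect comparison stands beside it, and the 85% power belongs to an unadjusted comparison

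*Combined protocol and SAP*

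**What the plan says.** In section 4, Analysis, Aim 3a, the plan states: "The tertiary outcomes are change in EE and energy intake from baseline to 36 wk". It then gives one EE model, introduced as an example: an ANCOVA of change in EE to week 36, specified as "treatment as the factor of interest and Δ BMI and Δ energy intake included as covariates as both might affect EE independently of drug". For energy intake it promises a model of the same kind, without a covariate list. The expected result is also worded as an EE increase after this adjustment, and Specific Aim 3 A hypothesises that "GLP1RA will normalize homeostasis by increasing EE in relation to energy intake".

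On the covariates, the Aim 1 expected result reads "We expect GLP1RA treatment will reduce BMI (primary efficacy endpoint", and Table 3 shows a standardised difference of -1.12 for % change in BMI. For intake, the Introduction says "Peripheral administration of GLP-1 or GLP1RA reduces blood glucose and energy intake in humans and rodents", and Aim 1 expects more satiety, "assessed by hunger VAS as well as fat and total calorie intake at free buffet test meal". Aim 3a gives no expected direction for the 24-hour recall measure that serves as the covariate.

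The power paragraph claims 85% with 19 evaluable subjects per group for a difference of about one pooled SD of the change.

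**The concern.** A covariate measured after randomisation and altered by treatment takes part of the treatment effect with it. Conditioning on it also gives up the protection of randomisation. The adjusted coefficient is a direct drug effect on EE only under two conditions:

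- BMI or intake change and EE change share no unmeasured cause.
- EE change does not act back on BMI or intake.

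The plan states neither. Its rationale, that both covariates may affect EE apart from the drug, does not deal with the drug's expected effect on BMI.

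At stake is whether the trial can say if EE itself differed between arms. Change in EE is a named outcome, yet the adjusted coefficient alone could suggest a rise that did not occur, hide a fall that came with weight loss, or understate a real rise. The 85% would also be read as the power of the planned model, which it is not.

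**Working it through.** **1. Is a total-effect EE analysis stated elsewhere?** No. The repeated-measures model under Aim 2 covers secondary endpoints. Table 1 lists EE without a model. The 6- and 18-week exploratory analyses in Aim 3a concern intake only.

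**2. Reproducing the plan's figures.** Inputs from Aim 3a and the general analysis text: 19 per arm, difference 1 SD of the change, two-sided 0.05.

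- Two-sample t-test: noncentrality = 1 × √(19/2) = 3.082, df = 36, power = 85.06%. This matches the stated 85%.
- SD of change at r = 0.5: SD × √(2(1 − 0.5)) = SD, so 162 and 155 kcal/d, as stated.
- Dropout: 24 × 0.8 = 19.2, so 19 evaluable, as stated.

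No residual SD, explained variance or treatment-covariate association enters. The 85% is therefore that of an unadjusted two-group comparison.

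**3. What the adjusted coefficient estimates.** From the documents: BMI effect −1.12 SD (Table 3, % change, baseline to 3 months, previous study). Assumed, not in the documents: within-arm BMI-EE correlation of size 0.3 or 0.5; intake effect 0.5 to 1.0 SD, with intake unrelated to EE within arm. In SD units:

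adjusted effect = total effect + 1.12 × (within-arm slope of EE change on BMI change)

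Rejection rates are simulated with 19 per arm, df 34.

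| Structure | Total effect | Adjusted effect (0.3 / 0.5) | Planned model rejects (0.3 / 0.5) | Unadjusted test rejects |
|---|---|---|---|---|
| Shared cause, no drug effect on EE | 0 | 0 + 1.12 × 0.3 = +0.34 / 0 + 1.12 × 0.5 = +0.56 | about 13-14% / 32-36% | about 5% |
| BMI change drives EE, no direct effect | −0.34 / −0.56 | 0 / 0 | about 5% | not needed here |
| EE change acts back on BMI, true rise 1 SD | +1 | 1 − 0.34 = 0.66 / 1 − 0.56 = 0.44 | about 36-40% / 22-25% | about 85% |

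At an SD of 162 kcal/d, the first row is 0.336 × 162 = 54 and 0.56 × 162 = 91 kcal/d. With Table 3's 1.39 SD for absolute BMI change instead of 1.12, the first row becomes +0.42 / +0.70 SD and about 16-17% / 43-46%.

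**4. Power of the planned model.** The target is a conditional effect of 1 SD with 19 per arm, simulated. R² is the assumed share of within-arm EE-change variance that the two covariates explain. The BMI effect is 1.12 SD, the intake effect 0.5 to 1.0 SD, and the covariate correlation 0 or 0.3.

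| R² | Power |
|---|---|
| 0 | about 63-71% |
| 0.09 | about 68-76% |
| 0.25 | about 76-82% |
| 0.4 | about 84-90% |

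Collinearity with treatment lowers power and explained variance raises it. The documents fix neither, so power may be below or above 85%.

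**The case against.** The strongest reply is that the conditional effect is what the investigators want. The Aim 3 A hypothesis, the wording of the power target and the expected result all speak of EE relative to intake or after adjustment. That stands: the model answers a declared question and should stay. A reader might infer that adjusting for post-randomisation change makes the analysis wrong. The documents do not support that; the gap is the missing total effect and the unstated assumptions.

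A reader might also point to the Introduction ("Critically, we do not know whether GLP1RA treatment affects EE and activity") and the energy-expenditure measures text ("There is no previous study examining the impact of GLP1RA treatment on EE in subjects with CP") as proof that the unconditional effect is a declared target. Those are background statements of a gap in knowledge. The firmer ground is that Aim 3a names change in EE itself as an outcome.

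Two further inferences go too far. One is that the planned model is biased towards the drug: the three structures above point in different directions, and nothing in the documents selects one. The other is that the aim is underpowered: that depends on how much variance the covariates explain, which is not given.

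It is fair, too, that the sizes are illustrative. The correlations, intake effects and R² are assumptions. The BMI effects are 3-month values from a study whose listed title concerns adolescents with severe obesity, not 36-week values in hypothalamic obesity. Finally, the endpoint is tertiary, and nothing prevents an unadjusted EE difference from being reported. But leaving it unspecified allows a choice between two differing coefficients after unblinding.

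**Conclusion.** The point holds as a minor one: a cheap improvement, with the power statement to be relabelled. Three things follow from the documents alone. The only stated EE model conditions on two post-randomisation changes, of which BMI at least is expected to respond to treatment. No total-effect comparison of EE is stated. The 85% is the power of an unadjusted comparison (85.06%).

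The size of any distortion rests on assumed correlations and a borrowed BMI effect. Over the range examined it is 0.34 to 0.56 SD with a 1.12 SD BMI effect. That is enough to matter when reading this outcome, but its direction is unknown. The primary analysis is unaffected.

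**What to change.** - Add, and report beside the planned model, a comparison of change in EE by treatment without post-randomisation covariates, preferably an ANCOVA with baseline EE. The stratification factors (site, age, gender) are optional with 38 evaluable subjects.
- List the covariates of the energy-intake model. If they include post-randomisation changes, add the same total-effect comparison with baseline intake.
- Keep the model with change in BMI and change in intake, label it as the conditional (direct-effect) analysis for Aim 3 A, and state its assumptions of no unmeasured shared cause and no reverse path.
- State that the 85% refers to the unadjusted two-group comparison.

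The cost is SAP wording and one more model per outcome; baseline EE and intake are already collected. The downside is two coefficients that may differ and need explaining, and a total effect that may be nil or negative if weight loss itself lowers EE. The two together show whether EE changed, but they do not identify the mechanism.
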